## 9. STUDY PROCEDURE

### 9.1. *Informed Consent / Subject enrollment*

No subject will be enrolled into the study who does not meet the inclusion/exclusion criteria and does not sign the current approved informed consent document. Informed consent will be obtained prior to collecting any data for the study. The original signed documents will be maintained by the investigator as a permanent part of the subject's medical records. A signed copy will be provided to the subject.

Subjects will each receive a discount on their surgery (\$2,000 down to \$900) as well as \$300 if they attend the 3-month visit.

### 9.2. *Surgery Procedures*

Following a full diagnostic examination (history, visual acuity, refraction, slit-lamp exam, fundus exam, topography, biometry, OCT of macula), patients who meet criteria can be admitted to the study. Preoperative photographs at the Verion will be taken for blood vessel axis alignment indicators. The patient will be brought to the operating room where standard phacoemulsification and IOL implantation will be performed. At the end of the procedure, a microscope photograph will be taken to document the orientation of the IOL.

### 9.3. *Visits and Examinations*

Subjects will participate in six study visits. Visits will include an uptake visit, two operative visits (one for each eye), and 6 postoperative visits (Visit numbers 3, 3A, 4, 4A, 5 and 6 below). The visit schedule, complete with window and associated CRF forms, are displayed in Table 9.3-1. Details of each study visit, including testing to be conducted, are provided below.

**Table 9.3-1. Visit Schedule**

Visit Number	Visit Name	Visit Window	CRF Number
1	Preoperative	-30 to 0 days from surgery	1
2, 2A	Operative (unilateral)	0 from surgery	2, 2A
3, 3A	1 Day Postoperative	1-2 days postoperative	3, 3A
4, 4A	1 Week Postoperative	7 ( $\pm 2$ ) days postoperative	4, 4A
5	1 Month Postoperative	30 ( $\pm 7$ ) days postoperative	5
6	3 Months Postoperative	90 ( $\pm 15$ ) days postoperative	6

All data collection will be completed through provided Case Report Forms (CRFs). All site personnel involved in the study will be trained in regard to conducting study-specific procedures. Case report forms will be identified by the subject number assigned at the time of randomization. No protected health information (PHI) will be included on any CRF. Subject identities will be removed at the initial visit so that there will be no further need to protect or destroy the information.

#### 9.3.1. Preoperative

The subject will complete an information and consent document. Inclusion and exclusion criteria will be applied to determine qualification for the study.

A medical history will be taken and exams will include the tests described below:

- manifest refraction,
- visual acuity,
- Preoperative photographs at the Verion will be taken for blood vessel axis alignment indicators

In addition, all site-specific, routine preoperative measures will be performed.

Measurements will be made as described in section 9.4 below.

The preoperative visit is expected to take about 30-45 minutes.

#### 9.3.2. Operative (Surgery)

The patient will be brought the operating room where standard phacoemulsification and IOL implantation will be performed. At the end of the procedure, a microscope photograph will be taken to document the orientation of the IOL.

Surgical findings will be recorded and any adverse events/serious adverse events (AEs/ SAEs) occurring during surgery will be noted at this visit. Any other problems during surgery and comments regarding surgery will be documented.

Any subject whose surgery is not completed successfully will be documented. These subjects will be monitored for safety but clinical performance data may be excluded from the analysis.

All study subjects will be placed on an appropriate antibiotic (Vigamox) and steroid (Durezol) drop QID for one week. A non-steroidal anti-inflammatory (Ilevro) drop will also be applied once a day for the first two weeks.

For the following three weeks, the steroid (Durezol) drop will be continued on a tapered dose.

#### 9.3.3. Postoperative 1 Day

All routine postoperative measures will be taken. In addition, the subject will undergo VA testing in accordance with the specifications below (Section 9.4). Intraocular pressure will also be measured. Adverse events will be monitored.

This visit is expected to take around 30 minutes to complete.

#### 9.3.4 Postoperative 1 Week

All routine postoperative measures will be taken. In addition, the subject will undergo VA testing in accordance with the specifications below (Section 9.4). Intraocular pressure (IOP) will also be measured. Adverse events will be monitored.

#### 9.3.5. Postoperative 1 Month

All routine postoperative measures will be taken. In addition, the subject will undergo manifest refraction, IOP measurement, VA testing and dilated Verion photographs to document the postoperative orientation of the IOL. Adverse events will be monitored.

#### 9.3.6. Postoperative 3 Months

All routine postoperative measures will be taken. In addition, the subject will undergo manifest refraction, IOP measurement, VA testing and dilated Verion photographs to document the postoperative orientation of the IOL. The patient's quality of vision will be measured using a validated, Rasch-scored questionnaire. A defocus curve in accordance with the specifications below (Section 9.4) will also be obtained at this visit. Adverse events will be monitored. An exit form will be completed.

#### 9.3.8. Exit Procedures

In the event of premature exit from the study, all study related examinations should be completed where possible. The Exit CRF should be completed, noting that the subject did not complete the study and the reason for premature study exit. If no premature exit from the study occurs, the Exit CRF should be completed at the end of Visit 6 (Postoperative 3 Months).

#### ***9.4. Study Methods and Measurements***

All routine testing and basic eye examinations should be carried out at each study visit. Abnormalities should be recorded in the CRF “Comment” section. Specific study examination procedures are outlined below.

##### **9.4.1. Manifest Refraction**

Perform a manifest refraction with a high contrast logMAR chart under photopic lighting conditions ( $>85 \text{ cd/m}^2$ ). Document refraction results with sphere, cylinder and axis readings. If uncorrected visual acuity is not improved by manifest refraction, use zero for sphere and cylinder and draw a line through the blank for the axis.

***Note:*** Each subject should be manually refracted to his/her best correction by an ophthalmologist, optometrist, or a skilled technician using a phoropter or trial lenses.

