## 8. STUDY DESIGN

### 8.1. Study Design

This study is a prospective, single center, open clinical trial to evaluate visual acuity at distance, intermediate and near as well as rotational stability of the Toric-ReSTOR IOL for 3 months after cataract surgery. Patients will be bilaterally implanted, with the Toric ReSTOR +2.5D model implanted in the dominant eye and the Toric ReSTOR +3.0D model implanted in the non-dominant eye. Patients will self-select for multifocal implantation. Toric IOL calculations will be completed with the Alcon Toric calculator, including the Barrett adjustment for posterior corneal astigmatism. The default surgically-induced astigmatism (0.1D) will be used for all calculations. Results from this study will be compared to outcomes data in the literature for the non-toric ReSTOR IOLs. Quality of vision will be measured using a validated, Rasch-scored questionnaire and compared to data available in the literature for non-toric ReSTOR lenses.

Subjects will be assessed pre-operatively and at 1 day, 1 week, 1 month and 3 months post-operatively.

Clinical evaluations will include measurement of visual acuity, manifest refraction, orientation of the toric ReSTOR IOL, defocus curve and quality of vision assessment.

The primary outcome measure will be the residual refractive cylinder.

Secondary outcome measures are as follows:

- Monocular and binocular Uncorrected and Best-corrected distance, intermediate (60cm) and near (40cm) visual acuity
- Postoperative orientation changes with the Toric ReSTOR IOL up to 3 months after surgery.
- Binocular Uncorrected and Best-corrected defocus curve (3 month visit).
- Quality of vision, measured with a subjective questionnaire.

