### **10.2. Statistical Methodology**

All data will be collected by the site and entered into a spreadsheet. Subjects will be assigned an ID number. Data analysis will be performed without patient identification. Statistical analysis will be performed using standard descriptive statistics and other tests as deemed appropriate based on the characteristics of the data to be analyzed. All statistical tests will be two-sided and interpreted at a 5% significance level.

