## **11. SAMPLE SIZE JUSTIFICATION**

Data in the literature suggests that the ReSTOR non-toric IOLs (+3.0D and +2.5D) implanted in a group of eligible eyes showed a residual refractive cylinder of  $0.40D \pm 0.32D$ . (Gundersen KG, Potvin R. Comparison of visual outcomes and subjective visual quality after bilateral implantation of a diffractive trifocal intraocular lens and blended implantation of apodized diffractive bifocal intraocular lenses. Clin Ophthalmol. 2016 May 10;10:805-11). We are looking for the toric IOLs to be non-inferior. We powered the study using that mean and SD, a power of 0.9, an alpha of 0.05, and a 0.25D non-inferiority margin. The mean residual refractive cylinders will be compared using a t-test between the two groups, with the mean and SD from the literature (blended bifocal group) and the mean and SD from the current study. The required sample size is 29 subjects. Allowing for 10% dropout we will plan to enroll 32 subjects.

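### Recording zero cylinder when refraction does not improve acuity can only lower the primary endpoint, and it favours non-inferiority unless the published comparator used the same rule

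*Combined protocol and SAP*

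**What the plan says.** Section 9.4.1 starts with a general instruction: "Document refraction results with sphere, cylinder and axis readings". It then makes an exception for eyes whose uncorrected acuity gains nothing from the refraction, where the examiner is to "use zero for sphere and cylinder and draw a line through the blank for the axis". The exception depends on acuity, and the section does not say whether one letter, one line or some other gain counts as improvement.

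Section 8.1 states: "The primary outcome measure will be the residual refractive cylinder". Sections 9.3.5 and 9.3.6 and Table 15.1 place postoperative manifest refraction at Visits 5 and 6. No objective refraction is listed, and nothing asks for the cylinder found before a zero is entered.

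Section 11 sets the hypothesis, "We are looking for the toric IOLs to be non-inferior", and the design values: "a power of 0.9, an alpha of 0.05, and a 0.25D non-inferiority margin". The comparator is a published blended-bifocal group at 0.40 ± 0.32 D. On the test it says: "The mean residual refractive cylinders will be compared using a t-test between the two groups". Neither that group's size nor its rule for recording refraction is given. Sections 3 and 6 add the aim of a normative standard for refractive outcomes.

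**The concern.** The recording rule acts directly on the variable that the trial tests, and it acts in one direction. A cylinder magnitude is zero or positive, and a smaller value is better. Any eye changed by the rule moves the study mean down, towards the claim the trial hopes to make. The comparator is a fixed published figure, so nothing in the trial offsets the movement.

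Two things are at stake. The first is the normative result: a mean that includes entered zeros is lower than the mean of the cylinders found, and the axis is lost for those eyes. This holds whatever the comparator did. The second is the non-inferiority comparison, which is affected only if the published group was recorded under a different rule.

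The rule could plausibly touch a fair number of eyes. Section 3 expects 75% of patients to reach 20/25 or better uncorrected, and Section 5 places the level of astigmatism that matters for visual quality above 0.50 D. Small cylinders may therefore often leave measured acuity unchanged. The study is open-label, and the undefined threshold leaves the decision to the examiner.

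**Working it through.** **Inputs from the documents (Section 11):** comparator mean 0.40 D, SD 0.32 D, margin 0.25 D, power 0.90, alpha 0.05, 29 subjects required.

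**Inputs assumed:** 29 in the comparator group, one value per subject, the share of eyes reset, and the distribution of cylinder.

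**1. Reproduce the plan's figure.** For a true difference of zero, n per group = 2 × [0.32 × (z for alpha + z for power) / 0.25]².
- One-sided 0.05: 2 × [0.32 × (1.645 + 1.282) / 0.25]² = 28.1, so 29. This is the plan's figure.
- One-sided 0.025: 2 × [0.32 × (1.960 + 1.282) / 0.25]² = 34.4, so 35. This is not the plan's figure.

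The sample size thus rests on one-sided 0.05, whereas Section 10.2 says: "All statistical tests will be two-sided and interpreted at a 5% significance level". Both levels are shown below.

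**2. Shift in the mean.** Shift = share of eyes reset × their mean cylinder as found.
- 10% reset at 0.25 D: 0.10 × 0.25 = 0.025 D, or 10% of the margin.
- 30% reset at 0.50 D: 0.30 × 0.50 = 0.15 D, or 60% of the margin.

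These shares are illustrations, not figures from the plan.

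**3. What is plausible at the margin.** False non-inferiority is judged where the true mean is 0.40 + 0.25 = 0.65 D. Assume a gamma distribution with mean 0.65 D and SD 0.32 D, rounded to 0.25 D steps. About 19% of eyes then fall at 0.25 D and about 34% at 0.50 D. Resetting every 0.25 D eye shifts the mean by 0.19 × 0.25 = 0.0475 D. A shift of 0.10 D needs all of those plus a share x of the 0.50 D eyes, where 0.0475 + x × 0.34 × 0.50 = 0.10, so x is about 0.31.

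**4. Simulation.** This uses the distribution from step 3 for the toric eyes, a gamma with mean 0.40 D and SD 0.32 D for the comparator, 29 against 29, and a t-test. The SD may change as zeros are added. The table gives the rate of false non-inferiority when the rule applies to the toric group only.

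| Eyes reset | One-sided 0.05 | One-sided 0.025 |
|---|---|---|
| None | about 4% | about 2% |
| Half of 0.25 D eyes | about 7% | about 3.5% |
| All 0.25 D eyes | about 11% | about 6% |
| All 0.25 D and half of 0.50 D eyes | about 33% | about 22% |

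**5. Same rule in both groups.** At one-sided 0.05 the rate is 1.1% to 4.4% across the patterns tried, so there is no inflation. Here the comparator has more 0.25 D eyes to lose (about 40% against 19%), so its mean usually falls further than the toric mean.

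**The case against.** The strongest reply is that this is a subjective refraction taken to best correction. If no lens combination improves acuity, writing plano may be read as defining the manifest result, not as discarding a measurement. The text allows that reading. It does not remove the point, because the general instruction asks for the readings and the exception turns on acuity, not on finding no cylinder.

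The trigger is also narrower than it first looks. A reader might infer that any well-seeing eye with 0.25 to 0.50 D is recorded as having none. The documents do not support that: sphere and cylinder together must fail to improve acuity, so an eye that gains from the sphere keeps its cylinder. Section 9.4.2 encourages guessing and reading down the chart, which helps to detect small gains. This limits the number of eyes affected and makes the lower rows of the table less likely.

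The comparison is biased only if the conventions differ, and the documents are silent on that. This stands. It also limits the remedy: if the published group used zeros, making as-found cylinder primary would create a mismatch against the toric lens.

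**Conclusion.** The point holds in a conditional form. What is certain from the documents is the direction: the rule can only lower the recorded mean cylinder or leave it unchanged, and so can only understate the normative value. That it favours non-inferiority is true only if the published group did not follow the same rule.

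The size is uncertain because the share of eyes reset is not in the documents. Under the stated assumptions a reasonable range is a rise from about 4% to between 7% and 11% at one-sided 0.05, or from about 2% to between 3.5% and 6% at one-sided 0.025. The lower end is more plausible.

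A reader might infer a much larger effect from a normal approximation with fixed SD. With SE = 0.32 × √(2/29) = 0.084, a 0.05 D shift gives 14.7% and a 0.10 D shift gives 32.5%, against 5%. Those figures assume one-sided 0.05. They also need slightly more than every 0.25 D eye reset, or every 0.25 D eye plus about 30% of the 0.50 D eyes. They describe an extreme case, and the documents do not support using them as the expected effect. Nor do the documents support an unconditional statement that false non-inferiority becomes more likely.

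The change is worth making because values that are never recorded cannot be recovered later.

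**What to change.** - **Recording.** In Section 9.4.1, require the sphere, cylinder and axis found at the refraction endpoint for every eye at Visits 5 and 6. Add a CRF tick box for acuity not improved, and define the gain that counts as improvement.
- **Normative result.** Report residual cylinder from the as-found values.
- **Non-inferiority comparison.** State in Section 11 how the published group recorded refraction. Use the matching version of the endpoint for the primary test, or the as-found version if the convention cannot be established. Give the other version as a sensitivity analysis. The claim need not depend on both versions agreeing.

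The cost is a short text change in Sections 9.4.1 and 11 and one CRF box. The refraction is already performed. The reported mean may be slightly less favourable.

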##### **9.4.2. Visual Acuity (VA)**

To obtain logMAR VA, ask subjects to begin reading the chart at a row where all letters are easily distinguishable. Have subjects continue to read rows with smaller letters and encourage subjects to guess at all letters in a line if at least one correct response was given on the previous row. Request subjects read rows until no letters on a row are read correctly or until all letters on a row are too indistinguishable to even be guessed.

Perform uncorrected and best-distance corrected visual acuity testing monocular and binocularly.

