##### *Distance VA*

Measure distance visual acuity using the 100% contrast ETDRS chart under photopic lighting at a distance of 4-6 m.

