##### *Intermediate VA*

Have the subject hold a Logarithmic ETDRS Visual Acuity Chart, “Chart 2”, at 60cm, using the 60cm cord held at the outer canthus as a reference. Record and score the subject’s visual acuity.

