##### *Near VA*

Conduct near testing with a Logarithmic ETDRS Visual Acuity Chart, “Chart 1” at 40 cm, using the 40cm cord held at the outer canthus as a reference. Visual acuity determined with the chart will be recorded and scored.

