## 15. STANDARD EVALUATION PROCEDURES

**Table 15.1. Proposed Visits and Study Assessments**

(visits are by patient, with both eyes tested)

Activity	Pre-operative	Operative	Postoperative			
	Visit 1	Visit 2, 2A	Visit 3, 3A	Visit 4, 4A	Visit 5	Visit 6
			1 Day	1 Week	1 Month	3 Month
Informed Consent	X					
Demographics	X					
General Information: Medical History	X					
Surgery		X				
Manifest Refraction	X				X	X
Uncorrected Distance VA (monocular and binocular)			X	X	X	X
Corrected Distance VA (monocular and binocular)	X				X	X
Uncorrected Intermediate and Near VA (monocular and binocular)					X	X
Distance-corrected Intermediate and Near VA (monocular and binocular)					X	X
Intraocular pressure			X	X	X	X
Verion photograph	X	X			X	X
Quality of vision questionnaire						X
Binocular Defocus curve (uncorrected and corrected)						X
Monitor for Adverse Events		X	X	X	X	X
Complete Exit Form 						X

 Complete Exit Form upon termination of subject participation, or at Visit 6, whichever occurs first.

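### At the 1- and 3-month visits one named chart each at 40 cm and 60 cm is read six times, with no alternate letters and no test order, so remembered letters can bias later acuity readings upward

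*Combined protocol and SAP*

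**What the plan says.** Section 9.4.2 sets the scope of testing: "Perform uncorrected and best-distance corrected visual acuity testing monocular and binocularly". It then gives one instruction per distance:

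- **60 cm:** "Have the subject hold a Logarithmic ETDRS Visual Acuity Chart, “Chart 2”, at 60cm".
- **40 cm:** "Conduct near testing with a Logarithmic ETDRS Visual Acuity Chart, “Chart 1” at 40 cm".
- **Distance:** "Measure distance visual acuity using the 100% contrast ETDRS chart under photopic lighting at a distance of 4-6 m". This names a type of chart, without a number or version.

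The same section tells the examiner to "encourage subjects to guess at all letters in a line if at least one correct response was given on the previous row", continuing until a row yields nothing.

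Table 15.1 places these tests by visit. Uncorrected and distance-corrected acuity, monocular and binocular, are both scheduled only at Visits 5 and 6 (1 and 3 months), and there at all three distances. Visit 1 has corrected distance acuity only. The 1-day and 1-week visits have uncorrected distance acuity only.

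Section 8.2, on minimizing bias, asks for uniform testing and encouragement across subjects. No section mentions alternate letters, rotation of charts, or the order of eyes and correction states.

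**The concern.** A subject who reads the same letters several times in one sitting may recall some of them. Recall helps most when an earlier reading went further down the chart than the later one could have gone unaided. That can happen here. Section 8.1 puts a different lens model in each eye, so the two eyes may resolve different rows at a given distance, and the corrected state may resolve more than the uncorrected one.

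Acuity is the first-listed secondary outcome. Section 6 aims at a normative standard for visual outcomes, and section 8.1 compares the results with published values for the non-toric lenses. With no concurrent arm tested the same way, a shift in the acuity readings is not cancelled within the study. It also cannot be removed after the data are collected.

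**Working it through.** **The plan's own figure.** The only computed figure is the sample size in section 11, for residual cylinder. With margin 0.25 D, SD 0.32 D, power 0.90 and one-sided alpha 0.05:

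n per group = 2 x 0.32² x (1.645 + 1.282)² / 0.25² = 28.07, rounded up to 29.

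This matches the plan. No acuity input enters it, so the present point does not touch it.

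**Readings per distance (section 9.4.2 and Table 15.1).**

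- Visits 5 and 6: 2 correction states x 3 viewing conditions (right eye, left eye, both) = 6 per distance, and 6 x 3 distances = 18 per visit.
- Visit 1: up to 3 at distance, corrected only.
- 1 day and 1 week: up to 3 at distance, uncorrected only.

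**Prior exposure within a visit.** If one letter set serves all six readings, they follow 0, 1, 2, 3, 4 and 5 earlier readings of the same letters, a total of 15. With one version each for right eye, left eye and binocular testing, and all uncorrected readings first, the three uncorrected readings follow none and the three corrected readings follow one each, a total of 3.

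**Swapping the two named charts.** Near and intermediate together need 6 + 6 = 12 readings per visit. Over two charts that is still 6 per chart, so swapping Charts 1 and 2 between 40 and 60 cm gains nothing.

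**Between visits.** By the windows in Table 9.3-1 (30 ± 7 and 90 ± 15 days), Visits 5 and 6 lie 75 - 37 = 38 to 105 - 23 = 82 days apart. Nothing in the documents supports recall over that interval, so the six readings of one visit are the relevant count.

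**Size.** The documents give neither a memory effect nor an acuity SD, so the bias cannot be calculated from them. The following is only an illustration. Assume normally distributed logMAR acuity, a true 75% at 0.1 or better (the expectation in section 3), and a uniform gain d in the scored reading. Then:

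observed rate = Φ(0.674 + d / SD)

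| Assumed gain d | SD 0.08 | SD 0.10 | SD 0.15 |
|---|---|---|---|
| 0 (scored reading comes first) | 75% | 75% | 75% |
| 0.02 logMAR | 82% | 81% | 79% |
| 0.04 logMAR | 88% | 86% | 83% |

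For scale, the 95% half-width of a 75% rate with 29 subjects is 1.96 x √(0.75 x 0.25 / 29) = 0.158, about 16 points. Section 3 does not say whether a monocular or a binocular reading defines the 20/25 rate, so the applicable row of the table is unknown.

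**The case against.** The strongest reply is that the readings that matter most may escape. The 20/25 expectation concerns uncorrected acuity. Section 9.4.2 lists uncorrected testing first, and section 9.4.1 treats uncorrected acuity as known when the refraction is judged. In that sequence corrected readings cannot help uncorrected ones within the visit. This stands in part. A listing is not an order, and even with uncorrected first, the second eye and the binocular reading still follow earlier readings of the same letters.

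Guessing also comes with no feedback, so working through unreadable rows does not reveal their letters, and a repeated wrong guess may gain nothing. This stands too: carry-over needs an earlier reading that was better than the later one. It limits the effect but does not exclude it, for the reasons given about the two eyes and the two correction states.

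The illustrated shifts lie within the 16-point sampling error. That is correct, but sampling error has no direction and shrinks with more subjects, whereas this bias would not. How the published comparison studies tested acuity is not stated. If they reused charts, part of the bias in the comparison would cancel.

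A reader might infer more than the text allows:

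- *That all three distances are tied to a single letter set.* Only 40 and 60 cm are. The distance wording neither requires nor rules out alternates.
- *That six readings occur at every visit.* They occur only at Visits 5 and 6.
- *That acuities and the 20/25 rate are in fact inflated, by a known amount.* The documents show a risk. Every figure for its size rests on assumed inputs, and zero is among the possible values.

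**Conclusion.** The gap is real but minor. Followed as written, section 9.4.2 has subjects read one named chart six times per visit at 40 cm and another six times at 60 cm, at 1 and 3 months, and leaves the letters at distance and the order of testing open. This creates an avoidable risk of upward bias in later readings, mainly second-eye, binocular and corrected acuities. The conclusion rests on the reading count and on the absence of any rotation or order, both of which can be checked in the text. It does not rest on the illustrative percentages.

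The consequence is limited to secondary outcomes. The primary outcome and the 29 subjects required for it are unaffected, and the 75% at 20/25 has no test or decision rule attached.

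**What to change.** In section 9.4.2:

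1. Replace the single named chart with different letter versions for right eye, left eye and binocular testing at each distance, each version calibrated for that distance.
2. Fix the order so that all uncorrected readings precede all corrected ones.
3. Add a field on the CRF for the chart version used.

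Do not rely on exchanging Charts 1 and 2 between 40 and 60 cm. That leaves six readings per chart, and the documents do not say that the two charts are interchangeable between distances.

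The cost is protocol wording, one CRF entry, two additional letter versions at each of 40 and 60 cm (and two at distance if only one is in use), and slightly more chart handling. Corrected readings would still follow one uncorrected reading of the same version. The change has to be made before acuity data are collected.
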